13.5.3 Accountability of Investigational Product

The IP is to only be prescribed by the principal investigator or his/her named sub-investigator(s), and is to only be used in accordance with this protocol. The IP must only be distributed to subjects properly qualified under this protocol to receive IP.

The investigator must keep an accurate accounting of the IP received from the supplier. This includes the amount of IP dispensed to subjects, amount of IP returned to the investigator by the subjects, and the amount returned or disposed upon the completion of the study. A detailed inventory must be completed for the IP.

13.5.4 Return or Disposal of Investigational Product

All IP will be returned to the sponsor or their designee or destroyed at the study site. The return or disposal of IP will be specified in writing.

13.6 Recording of Data on Source Documents and Case Reports Forms (CRFs)

The investigator is responsible for ensuring that study data is completely and accurately recorded on each subject's CRF, source document, and all study-related material. All study data should also be attributable, legible, contemporaneous, and original. Recorded datum should only be corrected in a manner that does not obliterate, destroy, or render illegible the previous entry (e.g., by drawing a single line through the incorrect entry and writing the revision next to the corrected data). An individual who has corrected a data entry should make clear who made the correction and when, by adding to the correction his/her initials as well as the date of the correction.

Data entry of all enrolled and randomized subjects will use software that conforms to 21 CFR Part 11 requirements, and will be performed only by staff who have been trained on the system and have access to the system. Data will not be entered for screen failure subjects. An audit trail will be maintained within the electronic system to capture all

changes made within the eCRF database. After the end of the study and database lock, compact discs (CDs) containing copies of all applicable subjects' eCRFs will be provided to each Investigator Site to be maintained on file by the Investigator.

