6 OVERALL STUDY DESIGN

6.1 Overall Design

This is a multicenter, double-masked, vehicle-controlled, randomized, parallel group study carried out in 2 stages (Stage 1: AXR-159 Ophthalmic Solution (30 mg/mL or 50 mg/mL) dosed three-times daily (TID) or twice-daily (BID); Stage 2: AXR-159 Ophthalmic Solution (3 mg/mL, 30 mg/mL or 50 mg/mL) dosed three-times daily (TID) or twice-daily (BID)).

For both Stages 1 and 2, patients with signs and symptoms of DED will be randomly assigned in a 1:1 (Stage 1) or up to a 2:2:2:2:1:1:1 (Stage 2) ratio to receive either a single concentration of AXR-159 Ophthalmic Solution or AXR-159 Ophthalmic Solution Vehicle. A screening visit will be followed by a baseline period where subjects will dose with AXR-159 Ophthalmic Solution Vehicle for 14 days. At the end of the baseline period patients who still exhibit signs and symptoms of DED will be enrolled into a 3-month treatment period (See [Appendix 1](#) for study visit structure across Stages 1 and 2 and [Figure 6.1-1](#) for the study flow diagram). If only a single dosing regimen is selected for Stage 2 a 1:1:1:1 regime may be selected: AXR-159 Ophthalmic Solutions and AXR-159 Ophthalmic Solution Vehicle.

[figure not shown]
When the 10th patient enrolled in Stage 1, Cohort 1 (8 patients on AXR-159 Ophthalmic Solution 50 mg/mL TID and 2 patients on vehicle TID) completes the Week 2 visit, a Data Review Committee (DRC) will evaluate all available safety data. If AXR-159 Ophthalmic Solution 50 mg/mL TID is safe and well tolerated the DRC will recommend

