10.1.4 Procedures for Final Study Entry

Subjects must meet all inclusion and none of the exclusion criteria.

10.1.5 Methods for Assignment to Treatment Groups:

Prior to initiation of study run-in (at Visit 1), each subject who qualifies for entry will be assigned a screening number. All screening numbers will be assigned in strict numerical sequence at a site and no numbers will be skipped or omitted. If all inclusion and exclusion criteria are met at Visits 1 and 2, each qualifying subject will then be assigned a randomization number at the end of Visit 2.

A randomization schedule will be provided to each investigational site. The randomization schedule will use block randomization stratified by site, such that there will be an approximate equal number of subjects assigned to each of the two treatment arms at each site for the Stage 1, Expansion Cohort. For Stage 1, Cohorts 1-3 patients with signs and symptoms of DED will be randomly assigned in a 4:1 ratio to receive either a single concentration of AXR-159 Ophthalmic Solution or AXR-159 Ophthalmic Solution Vehicle. The site staff will dispense to the patient the study kit labelled with the corresponding randomization number. The randomization number will be recorded on the patient's source document and eCRF. New kits will be dispensed at Visits 2, 3, and 4 based on the subject's randomization. The Sponsor, Investigators, and study staff will be masked during the randomization process and throughout the study.

During the run-in period, the patients will all be supplied with AXR-159 Ophthalmic Solution Vehicle. Patients will be informed that they will receive only vehicle during the 2-week run-in period. Following the run-in period the patient, site personnel, the sponsor and patients will be masked to the treatment assignment for the 3 month treatment period. All study medication will be provided in identical unit of dose vials and cartons to maintain masking of the study.

For both Stages 1 and 2, patients with signs and symptoms of DED will be randomly assigned in a 4:1 (Stage 1, Cohorts 1-3) ratio, a 1:1 (Stage 1, Expansion Cohort) ratio, or to a 2:2:2:2:1:1:1 (Stage 2) ratio to receive either a single concentration of AXR-159 Ophthalmic Solution or AXR-159 Ophthalmic Solution Vehicle.

For the expansion cohort in Stage 1 and Stage 2, subjects will be randomized by strata as follows:

- Site
- Baseline eye dryness score ≥ 60 , < 60
- Baseline inferior corneal staining > 1.5 , ≤ 1.5

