10.3.1.5 Visit 5: 3 Month Follow-up (Day 85 ± 2 Days)

Pre-CAE®

- Study drug collection
- Medical/medication history update
- Urine pregnancy test (for females of childbearing potential)

- Patient symptoms using the visual analog scale
- Ocular Discomfort Score
- OSDI
- SANDE
- BCVA with manifest refraction
- Vital signs
- Bulbar conjunctival hyperemia scores (Ora Calibra® Conjunctival Redness for Dry Eye Scale)
- Slit-lamp biomicroscopy
- Tear Collection (selected sites)
- Oculus Keratograph 5® procedures: TBUT and tear meniscus height (selected sites)
- TFBUT
- Sodium fluorescein corneal staining, using the Oxford scale and Ora Calibra® scales
- Lissamine green conjunctival staining, using the Oxford scale
- 15+ minute wait from end of Lissamine staining to start of Schirmer's Test
- Schirmer without anesthesia
- 90-minute CAE® exposure;
 - Ora Calibra® Ocular Discomfort Scale upon entering the CAE® and every 5 minutes thereafter;

Post-CAE®

- Patient symptoms using the Visual Analog Scale
- Ocular Discomfort Score

- Bulbar conjunctival hyperemia scores (Ora Calibra® Conjunctival Redness for Dry Eye Scale)
- Slit-lamp biomicroscopy
- TFBUT
- Sodium fluorescein corneal staining, using the Oxford scale and Ora Calibra® scales
- Lissamine green conjunctival staining, using the Oxford scale
- Intraocular pressure (IOP)
- Ophthalmoscopy
- Blood sample collection for Hematology and Chemistry
- Urine sample collection for Urinalysis
- Administer AXR-159 Ophthalmic Solution or vehicle in both eyes (must NOT be done before blood and tear sample collection)
- Ora Calibra® Drop Comfort Assessment
- Adverse event query
- Study Exit

Adverse Events (AEs) (both elicited and observed) will be monitored throughout the study. All AEs (both elicited and observed) will be promptly reviewed by the investigator for accuracy and completeness. All AEs will be documented on the appropriate CRF.

If a female becomes pregnant during the study, the investigator will notify AxeroVision Inc. immediately after the pregnancy is confirmed and the patient will be exited from the study after appropriate safety follow-up. The investigator will (1) notify the patient's physician that the patient was being treated with an investigational drug (AXR-159 Ophthalmic Solution), and (2) follow the progress of the pregnancy. The investigator must document the outcome of the pregnancy and provide a copy of the documentation to AxeroVision Inc.

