11.5 Type and Duration of the Follow-up of Subjects after Adverse Events

Any serious adverse event occurring during the study period (beginning with informed consent) and for at least 12 weeks after the last dose of study drug must be immediately reported, but no later than 24 hours after learning of a serious adverse event. Serious adverse events must be reported to AxeroVision Inc. (or Agent of AxeroVision Inc.) as listed on the AxeroVision Inc. Study Contacts Sheet and recorded on the serious adverse event form. All patients with a serious adverse event must be followed up and the outcomes reported. The investigator must supply AxeroVision Inc. and the IRB/IEC with any additional requested information (e.g., autopsy reports and discharge summaries).

In the event of a serious adverse event, the investigator must:

1. Notify AxeroVision Inc. immediately by fax or email using the serious adverse event form (contact details can be found on page 1 of the serious adverse event form); phone numbers and relevant AxeroVision Inc. personnel contacts are also on the front page of the protocol.
2. Obtain and maintain in his/her files all pertinent medical records, information, and medical judgments from colleagues who assisted in the treatment and follow-up of the patient.
3. Provide AxeroVision Inc. with a complete, written description of the adverse event(s) on the serious adverse event form describing the event chronologically, including any treatment given (e.g., medications administered, procedures performed) for the adverse event(s). Summarize relevant clinical information about the event: signs, symptoms, diagnosis, clinical course and relevant clinical laboratory tests, etc. Include any additional or alternative explanation(s) for the causality which includes a statement as to whether the event was or was not related to the use of the investigational drug.

4. Promptly inform the governing IRB/IEC of the serious adverse event as required by the IRB/IEC, local regulations, and the governing health authorities.

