7.4 Safety

The Safety population includes all randomized subjects who have received at least one dose of the investigational product. The Safety population will be analyzed for all safety assessments. Subjects in the Safety population will be analyzed as treated.

8. General Statistical Considerations

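### Protocol 13.6 bars data entry for screen failures, so non-serious adverse events in subjects exposed to the CAE and run-in vehicle but never randomised are missing from the eCRF and every planned safety output

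*Protocol*

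**What the plan says.** Protocol Section 13.6 sets the data-entry rule: "Data will not be entered for screen failure subjects". The same paragraph describes whose data are entered: "Data entry of all enrolled and randomized subjects will use software that conforms to 21 CFR Part 11 requirements".

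Other protocol sections set a recording duty with no exception for subjects who are not randomised. Section 10.3.1.5 says of events monitored throughout the study: "All AEs will be documented on the appropriate CRF". Sections 11.1 and 11.3 repeat that duty. Section 8.2, which covers the screening laboratory tests, sends clinically significant abnormalities to an adverse event page of the eCRF. For serious events, Section 11.5 opens the window at consent: "Any serious adverse event occurring during the study period (beginning with informed consent"). It routes them to the sponsor on a dedicated form.

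On timing, Section 6.1 places enrolment after the vehicle run-in: "At the end of the baseline period patients who still exhibit signs and symptoms of DED will be enrolled into a 3-month treatment period". Section 10.1.5 places randomisation later still: "each qualifying subject will then be assigned a randomization number at the end of Visit 2".

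SAP Section 7.4 defines the safety analysis set: "The Safety population includes all randomized subjects who have received at least one dose of the investigational product". SAP Section 8.4 bases listings on randomised subjects unless otherwise specified.

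**The concern.** A ban on entering screen-failure data does little harm when failures occur before anything has been done to the subject. Here they can occur after a 90-minute environmental challenge and two weeks of drops in both eyes. Table 9.1.1-1 lists the vehicle under investigational product, and SAP Section 16.1 counts vehicle given at any stage as study drug.

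Adverse event queries are scheduled after the CAE at Visit 1 and again at Visit 2. Sites will therefore hold the information and face opposite instructions on whether to enter it.

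Safety and tolerability are primary objectives in both stages. If the ban is followed, the account of how subjects tolerated the vehicle and the CAE during the run-in comes only from those who went on to randomisation. Anyone who left because of the drops or the chamber would be absent from it.

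**Working it through.** **Step 1: is a Visit 2 failure a screen failure?** The term is not defined, so it has to be read from usage.

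- Section 7.1 plans about 200 screened for about 100 randomised (Stage 1) and about 660 for about 330 (Stage 2), at a failure rate of about 50%. Check: 100 / (1 − 0.5) = 200 and 330 / (1 − 0.5) = 660. Both reproduce, so the rate counts everyone screened but not randomised.
- Section 6.1 puts enrolment after the run-in, and Section 10.1.5 requires the criteria to be met at both visits before a randomisation number is given.
- A subject who no longer qualifies at Visit 2 is therefore neither enrolled nor randomised, and falls under the ban.

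**Step 2: what has that subject been exposed to?** Section 10.3.1.1 and Appendix 1 give the 90-minute CAE, then dispensing and instillation of vehicle at Visit 1. Over 14 days that is 14 × 2 = 28 applications (BID) or 14 × 3 = 42 (TID). Section 10.3.1.1 also repeats the eligibility review after the CAE, so some Visit 1 failures will have had the CAE without the vehicle.

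**Step 3: do the recording rules agree?** They do not.

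- Section 13.6: nothing is entered.
- Sections 10.3.1.5, 11.1 and 11.3: all adverse events go on the CRF.
- Section 8.2: a clinically significant screening laboratory result goes on an eCRF page. A subject excluded for such a result needs the very entry that 13.6 forbids.
- Section 11.5: serious events go on a separate form. This does not depend on eCRF entry and does not conflict with 13.6.

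**Step 4: does the SAP recover the events?** The Safety population is limited to randomised subjects (7.4), disposition starts at randomisation (Section 9), and no listing in SAP Section 21 is marked as covering anyone else. Lifting the ban alone would not put these events into any planned output.

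**Step 5: size.** Planned screen failures are (200 − 100) + (660 − 330) = 100 + 330 = 430, against 430 randomised. The documents do not split failures by visit, so the Visit 2 share s is an assumption. Vehicle-exposed failures are m = 430 × s, and their share of everyone given run-in vehicle is m / (430 + m).

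- s = 10%: m = 43; 43 / 473 = 9%
- s = 25%: m ≈ 108; 107.5 / 537.5 = 20%
- s = 50%: m = 215; 215 / 645 = 33%
- s = 60%: m = 258; 258 / 688 = 38%

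If 2% to 10% of these subjects had an adverse event during the run-in (also an assumption), the number with an event missing from the database runs from 43 × 0.02 ≈ 1 to 258 × 0.10 ≈ 26. Stage 2 depends on a DRC recommendation. Stage 1 alone has 100 planned failures, so 10 to 60 exposed subjects on the same shares.

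**The case against.** The strongest reply is that little is lost. Much of it stands, and it rules out several stronger readings.

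- A reader might infer that all adverse events in these subjects disappear. The documents do not support that. Serious events are reported from consent on their own form (11.5), Section 11.1 requires events in source documents, and Section 11.3 requires reporting to Ora, the sponsor and the IRB/IEC as applicable rules demand. The gap is non-serious events, in the database and the planned outputs.
- A reader might infer that the trial will hold no run-in safety data. It will: the roughly 430 planned randomised subjects all take the run-in vehicle, and SAP Section 16.1 keeps events that began before treatment in the adverse event listings.
- A reader might infer that the DRC cannot see these events. Sections 6.3 and 13.7.6 leave its data to a charter that is not among these documents, so this cannot be settled either way.
- A safety population of randomised, dosed subjects is not an error, and selecting subjects through a vehicle run-in is deliberate (Section 6.2). Failing the sign and symptom thresholds at Visit 2 is an ordinary reason to drop out, and nothing shows that intolerance is a common one.
- A subject who stops during the run-in because of an event might be handled as a discontinuation, with the reason on the eCRF (7.5, 10.6.2), rather than as a screen failure. The documents leave this open.

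The last point argues for defining the term. None of the points removes the contradiction between 13.6 and the recording sections, or supplies a planned output for these subjects.

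**Conclusion.** The point holds as an internal contradiction with a bounded consequence. Followed as written, Section 13.6 keeps the non-serious adverse events of exposed, non-randomised subjects out of the eCRF, and the SAP leaves them out of every safety table and listing. The trial could then describe run-in tolerability of the vehicle and the CAE only among subjects who were randomised.

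It does not follow that the safety comparison of active with vehicle is biased. These subjects leave before assignment and receive only vehicle, so their absence cannot differ by arm. Sample size, power and alpha are untouched.

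The 430 planned failures follow from the protocol's own figures. The 43 to 258 vehicle-exposed subjects rest on the assumed 10% to 60% Visit 2 share, and the count of subjects with an event rests on a further assumed incidence. The contradiction itself depends on neither. Given a primary safety and tolerability objective and a cheap remedy, it should be corrected.

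**What to change.** 1. Define screen failure in the protocol. State whether it covers subjects who no longer qualify at Visit 2 and those who stop during the run-in.
2. Replace the sentence in Section 13.6, for example with: *For any subject exposed to the CAE or to run-in vehicle who is not randomised, run-in dispensing, the reason for failure and all adverse events will be entered in the eCRF.* This brings 13.6 into line with Sections 8.2, 10.3.1.5, 11.1 and 11.3.
3. Add to SAP Sections 16.1 and 21 a listing of adverse events in these subjects, kept apart from treatment-emergent events and from the Safety population, whose definition need not change.

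The cost is a few eCRF fields for exposed failures, one listing and the extra data entry. The adverse event queries are already scheduled, and the SAP's subject identifier is built from the screening number, so these subjects can be identified without a new numbering scheme. No efficacy analysis changes.

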13.7 Handling of Biological Specimens

13.7.1 Handling of Biological Specimens

All samples will be returned to AxeroVision Inc. or AxeroVision Inc. designee at the completion of the study. AxeroVision Inc. shall have full ownership rights to any biological specimens/samples derived from the study.

13.7.2 Blood and Urine Samples for Safety Analysis

Samples of blood (non-fasting) will be evaluated for blood chemistry, and hematology [including complete blood count with differential and HbA1c] at a centralized clinical laboratory (ie, ICON Central Laboratory Services, Whitesboro, New York, USA) with certification from a recognized accreditation agency. Details of sample collection are found in the procedure manual.

13.7.3 Blood Samples for Pharmacokinetic Analysis

Blood samples obtained at the study sites will be analyzed for AXR-159 concentrations by an AxeroVision Inc. qualified laboratory (i.e., Intertek Pharmaceutical Services, El Dorado Hills, California, USA) using a validated method. This laboratory has been qualified by AxeroVision Inc.'s Bioanalytical Sciences department to conduct analysis of clinical samples. Details of sample collection and handling are found in the procedure manual.

13.7.4 Tear Samples

Details of sample collection and handling are found in the procedure manual.

All samples will be stored at the clinical site or at ICON until shipment to the bioanalytical laboratory.

13.7.6 Safety Oversight

Safety oversight will be under the direction of a DRC composed of individuals with the appropriate expertise (see Section 6.3). Members of the DRC should be independent from the study conduct and free of conflict of interest, or measures should be in place to minimize perceived conflict of interest. The DRC will meet at least monthly to assess safety and efficacy data on each arm of the study. The DRC will operate under the rules of an approved charter that will be written and reviewed at the organizational meeting of the DRC. At this time, each data element that the DRC needs to assess will be clearly defined. The DRC will provide its input to AxeroVision Inc., the IRB and regulatory authorities as necessary.

13.7.7 Clinical Monitoring

A representative of Ora, Inc. will monitor the study on a periodic basis. The determination of the extent and nature of monitoring will be based on considerations such as the objective, purpose, design, complexity, blinding, size, and endpoints of the study. Authorized representatives of AxeroVision Inc., Ora, Inc., or regulatory authority representatives will conduct onsite visits to review, audit, and copy study-related documents. These representatives will meet with the investigator(s) and appropriate staff at mutually convenient times to discuss study-related data and questions.

13.7.8 Quality Assurance and Quality Control

Each clinical site will perform internal quality management of study conduct, data and biological specimen collection, documentation and completion. An individualized quality management plan will be developed to describe a site's quality management.

Quality control (QC) procedures will be implemented beginning with the data entry system and data QC checks that will be run on the database will be generated. Any missing data or data anomalies will be communicated to the site(s) for clarification/resolution.

Following written Standard Operating Procedures (SOPs), the monitors will verify that the clinical trial is conducted and data are generated and biological specimens are collected, documented (recorded), and reported in compliance with the protocol, International Conference on Harmonisation Good Clinical Practice (ICH GCP), and applicable regulatory requirements (e.g., Good Laboratory Practices (GLP), Good Manufacturing Practices (GMP)).

The investigational site will provide direct access to all trial related sites, source data/documents, and reports for the purpose of monitoring and auditing by the sponsor, and inspection by local and regulatory authorities.

